6.3.2. ECG Recordings

ECG recordings will be performed at the following timepoints:

To ensure the patient's safety

- At the baseline assessment: a single ECG tracing will be analysed by the central cardiologist to assess potential rhythm or conduction disorders and to assist the Investigator in screening patients.
- On D2, D3 and D4 prior to administration of fexinidazole (along with the triplicate ECG tracings on D4 H23): a single ECG will be analysed by the Investigator to check the QTcF interval (QT interval corrected using Fridericia's formula), calculated automatically. If the value for the QTcF-interval is higher than 500 ms, a second ECG tracing must be collected after a 10-to-20 minute rest. If the value is confirmed, the patient must be withdrawn from the study, and no further doses of fexinidazole are to be administered. The ECG tracings will not be reviewed systematically by the cardiologist.
- On D11 (EOT): single ECG.
- During hospitalisation and the follow-up period, additional ECG tracings may be collected at the discretion of the Investigator.

To assess QT interval

- Triplicate ECG tracings, 2 minutes apart, will be recorded at the following timepoints:
 - o At the baseline assessment;
 - On D4 4 hours after intake of fexinidazole;
 - on D4H23, i.e. one hour before intake of the IP on D5, this ECG should also be used for the patient's safety assessment prior to administration of fexinidazole;
 - o on D10 between 2 and 3 hours after intake of fexinidazole.

Repeat ECG

If the central cardiologist issues an alert at the last ECG assessment, e.g. for QTinterval prolongation or change in ECG pattern, the Investigator will record an additional ECG at the EOH visit, i.e. prior to discharge. If the alert is maintained at the EOH, the Investigator must record an additional ECG at the 3-month followup visit.

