5.3. Treatment Allocation

All patients will receive the same treatment.

The number of the treatment pack will be recorded in the patient's file and on the pharmacy log sheet.

Patient participation in the study will be considered to be finished when the last protocol-planned visit has been performed, i.e. the last visit at M18.

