8.2. Rules for Definitive Discontinuation of Treatment

The Investigator will discontinue the IP in the following cases:

- Severe skin reaction;
- ALAT or ASAT exceeding 8 x ULN;
- ALAT or ASAT exceeding 3 x ULN accompanied by total bilirubin exceeding 2 x ULN;
- ALAT or ASAT exceeding 3 x ULN accompanied by fatigue, nausea, vomiting, right upper quadrant pain or tenderness, fever, rash and/or eosinophilia exceeding 5%;
- QTcF interval ≥ 500 msec prior to intake of fexinidazole on D2, D3, D4 or D4H23), confirmed by a second ECG recorded after the patient has been in the resting position for at least 10 to 20 min;
- Any condition that, in the opinion of the Investigator, requires treatment discontinuation for medical reasons.

If a patient is withdrawn from the study before the end of treatment, the physician will make all necessary arrangements to ensure that s/he receives appropriate treatment for the condition in question.

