8.3. Patient Withdrawal from the Study and Replacement of Patients

A patient may be withdrawn from the study in the following cases:

- withdrawal of consent by the patient or his/her legal representative;
- study termination by the Sponsor.

If the patient or his/her legal representative withdraws his/her consent, no further evaluations will be performed, with the exception of safety data, which must be collected whenever possible.

Data collected prior to withdrawal of the patient will be taken into account in the efficacy and safety analyses.

If a patient decides to withdraw from the study, the reason must be recorded in the CRF. If a patient is withdrawn from the study due to an AE, all measures must be taken as needed to clearly document the outcome of the AE. Patients withdrawn from the study will not be replaced.

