8.4. Patients Lost to Follow-up

If a patient does not attend a protocol-planned visit, all necessary measures must be taken to contact him/her. In all cases, all necessary measures must be taken to document the outcome of the patient's condition, if possible.

9. Data Analysis and Statistical Methods

A full Statistical Analysis Plan (SAP) will be prepared prior to database lock. It will provide a detailed description of the statistical methods.

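### After a confirmed QTcF at the D2 to D4H23 checks, sections 6.3.2 and 8.2 of the protocol differ on action and threshold; 2.2.2 and 6.5.1 differ on whether a symptom-free ECG finding is an AE.

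*Protocol*

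**What the plan says.** **Action on a confirmed QTcF.** Protocol section 6.3.2 has the Investigator check the automatically calculated QTcF on D2, D3, D4 and D4H23, before the next dose. A value above 500 ms is repeated after a rest. Then: "If the value is confirmed, the patient must be withdrawn from the study, and no further doses of fexinidazole are to be administered". That is two orders, one about the study and one about the drug.

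Section 8.2 gives the rules for definitive discontinuation of treatment. It opens with "The Investigator will discontinue the IP in the following cases" and lists "QTcF interval ≥ 500 msec prior to intake of fexinidazole on D2, D3, D4 or D4H23", confirmed by a second ECG after rest. It orders nothing about leaving the study.

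Section 8.3 introduces its list with "A patient may be withdrawn from the study in the following cases". The list has two items, withdrawal of consent and termination by the sponsor. Later in the same section there is a sentence on what to document when a patient is withdrawn because of an AE.

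**AE status.** Section 2.2.2 states that ECG abnormalities without clinical symptoms are not reported as AEs and that ECG changes are analysed separately. Section 6.5.1 includes a clinically significant ECG finding in the definition of an AE and sets no symptom condition.

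**The concern.** A site with a confirmed reading has to act before the next dose, usually without a cardiologist, since 6.3.2 says these tracings are not systematically reviewed by one. It needs a single instruction, and the protocol gives two.

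Read as written, 6.3.2 could take a partly treated child with a marked QT signal out of the planned visits. That child's QT recovery and 12-month HAT outcome are both of interest. Under 9.2 a missing 12-month outcome that does not meet the probable-success criteria is counted as a failure.

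The AE question matters because 9.9 reports AEs leading to treatment discontinuation, and 10.1 names the same events among what the DSMB reviews. If a site follows 2.2.2, a QTcF stop without symptoms may not enter that output. If it follows 6.5.1, it does. The same event would be counted differently from site to site.

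Neither matter can be left to an analysis plan. One is a bedside instruction and the other decides what is entered on the AE page of the CRF.

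**Working it through.** The point is textual, and it disputes no figure in the plan. The protocol gives no expected number of QTcF stops.

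**Step 1. The two QTcF rules side by side.**

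| Item | 6.3.2 | 8.2 |
|---|---|---|
| Checks | D2, D3, D4, D4H23 | D2, D3, D4, D4H23 |
| Trigger | above 500 ms | 500 ms or more |
| Repeat ECG after rest | yes | yes |
| Fexinidazole | stopped | stopped |
| Study | withdrawal ordered | no order |

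The rules agree on the checks, the repeat and stopping the drug. They differ in the trigger and in whether the child leaves the study. A confirmed reading of exactly 500 ms stops treatment under 8.2 and calls for nothing under 6.3.2.

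**Step 2. The two AE rules.** Take a child without symptoms whose confirmed QTcF ends treatment. Under 2.2.2 there is no AE. Under 6.5.1 there is one if the finding is clinically significant, and a finding that forces a permanent stop is hard to call anything else. The outputs divide as follows:
- Depends on the AE label: the 9.9 output on AEs leading to discontinuation, and the matching DSMB item in 10.1.
- Does not depend on it: disposition (9.5), exposure of those who stop early (9.7), ECG abnormalities by timepoint (9.9), QTcF categories and change from baseline (9.10).

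**Step 3. How many children.**
- Rise needed: 4.3 excludes a QTcF of 450 ms or more, so the rise to 500 ms exceeds 500 − 450 = 50 ms.
- Earlier human studies (1.8): prolongation was usually around 30 ms, and one of more than 4000 recordings rose by 60 ms.
- Adults in DNDiFEX004 (1.10): QTcF stayed below 500 ms, including at peak concentration. The observed rate is zero.
- Upper bound: the number of adults behind that statement is not given. *Assuming* all of the roughly 125 adults on fexinidazole, the exact two-sided 95% upper limit for 0 of n is 1 − 0.025^(1/n). With n = 125 this is 1 − 0.025^(1/125) = 2.91%, or 0.0291 × 125 = 3.6 children. A smaller n would raise it. This is a bound, not an expected count, and it assumes that children respond as adults do.
- Exposure: a 20 kg child receives 1200/20 = 60 mg/kg on Day 1, which is 60/52.2 = 1.15 times the adult maximum in 1.11. Only children below 1200/52.2 = 23.0 kg exceed that maximum. Over the whole course the 20 kg child receives 8400/(20 × 10) = 42 mg/kg/day, equal to the adult maximum.

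**Step 4. Primary result.** The rule of 109 successes in 125 has exact one-sided alpha 0.0243 at a true rate of 80% and power 97.8% at 92%, in line with the 97.5% stated in 9.1. Neither changes with the wording. As an illustration only, one child counted as a failure solely because of withdrawal, with the other 124 succeeding at 92%, gives P(X ≥ 109) = 96.1%. Even this overstates the effect, because a child whose course is cut short and who then receives rescue treatment is a failure under 9.8.1 whether or not follow-up continues.

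**The case against.** **The two QTcF rules can be followed together.** Section 8.2 never says that the child stays in the study. It sits under the heading of withdrawal criteria, and its last sentence begins "If a patient is withdrawn from the study before the end of treatment". So a site may stop the drug and also withdraw the child without breaking 8.2. This is fair as far as it goes. But that sentence is conditional and orders no withdrawal, and the difference in threshold remains.

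**The list in 8.3 is not clearly complete.** A reader might infer that 8.3 forbids withdrawal for QTcF. It does not go that far, since it also mentions withdrawal due to an AE. Equally, that mention does not make withdrawal the rule for QTcF. It would reach a symptom-free case only if the finding is an AE, which 2.2.2 denies.

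**Follow-up need not be lost.** A reader might infer that the child disappears from the study. The documents do not support that as a certainty. Only withdrawal of consent carries the consequence that "no further evaluations will be performed, with the exception of safety data". Section 5.3 says "Patient participation in the study will be considered to be finished when the last protocol-planned visit has been performed", and for a missed visit 8.4 asks that "all necessary measures must be taken to document the outcome". Section 6.3.2 also provides repeat ECGs after a cardiologist's alert at the last ECG assessment. Section 6.5.9 continues follow-up of possibly related events after participation ends, but it stands under AE follow-up, so its help may depend on the disputed AE label.

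**The AE rules can be read as specific over general.** Section 2.2.2 may be a deliberate carve-out, with ECG data analysed on their own and details in a separate SAP (9.10). That is a possible reading, but 6.5.1 names ECG findings itself and does not refer to the carve-out.

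**Section 6.5.7.** A reader might infer that it classifies every Section 8 stop as an AE. It does not. It limits the Investigator's discretion over stopping treatment for an AE and is no part of this conflict.

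**The DSMB.** A reader might infer that the DSMB would not see such a case. Sections 6.5 and 10.1 have it review safety data generally, so its view is not confined to AE-driven stops.

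**Conclusion.** The inconsistency is real, and the point is minor. For the same checks the protocol gives two actions (withdraw from the study, or stop the drug only) and two thresholds (above 500 ms, or 500 ms and above). It also gives two AE rules for a symptom-free ECG finding.

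The consequence is a possibility: a child with a marked QT signal might leave planned follow-up, and a QTcF stop might be missing from one safety output while remaining visible in others. Few if any children are expected to be affected. The adult data point to zero, with an upper limit of 2.9% on the assumption of 125 adults with ECG monitoring and a similar response in children. The sample size, the primary test and the pass mark of 109 in 125 are unaffected. Nothing here supports a claim that the primary result is biased.

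**What to change.** Amend three sections:

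- **6.3.2:** *If a QTcF of 500 ms or more is confirmed, fexinidazole is permanently discontinued (see 8.2); the child remains in the study and attends all follow-up visits to 18 months unless consent is withdrawn.* This settles both the action and the threshold. Keeping the child in the study is a choice beyond pure reconciliation. It preserves the QT recovery checks and the 12-month outcome.
- **8.2, last sentence:** extend the duty to arrange appropriate treatment to patients who discontinue fexinidazole early, and keep the existing cover for those withdrawn from the study.
- **2.2.2:** add *except that an ECG finding leading to discontinuation of fexinidazole is recorded as an AE (6.5.1) and counted in 9.9.*

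The cost is amendment wording. The AE count might rise slightly, most likely by none.

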6.3.3. Laboratory Tests

A repeat urine pregnancy test will be performed at discharge, i.e. between D13 and D18 in girls \geq 12 years of age.

Blood biochemistry and haematology assessments will be repeated on D5, D8 and D11 (EOT visit). Safety biochemistry and haematology assessments will be performed 9 weeks after intake of the first dose on D1, only in patients who reach this visit from mid-December 2014 onwards. Safety haematology and biochemistry assessments will also be performed at the 6 month follow-up visit, only in patients who reach this visit from January or February 2016 onwards. Blood samples will be analysed in the laboratory in each centre using standard equipment specifically provided for the study by the Sponsor. Whenever possible, the samples should be collected from patients in the fasting state.

Parasitology testing requires 5 mL of whole venous blood or 4 mL of CSF. The blood sample should be analysed on an mAECT column within 30 minutes after collection. The CSF sample should be examined after MSC within 15 minutes after collection. The WBC in the CSF sample should be performed within 15 minutes after collection. It is necessary to collect 5 mL of CSF to perform the two tests.

Full haematological and biochemistry analyses require at least 0.5 mL of capillary or venous blood. Capillary blood collection considerably reduces the total quantity of blood collected as compared to classical techniques. However, because it is not always feasible, collection of venous blood is permitted. For each sample, 2 mL per tube should be collected, one tube containing EDTA for haematology and one tube containing heparin lithium for biochemistry.

The urine analyses performed at the baseline assessment and at the EOT visit, (as well as the pregnancy test on D-1, on D18 and at 3 months in women), require only a few millilitres (5-10 mL) If any abnormalities are found, additional urine analyses will be requested for further investigation and to determine whether or not the abnormality constitutes an AE.

During hospitalisation, additional safety assessments such as haematology, biochemistry or urine tests may be performed at the discretion of the Investigator in order to monitor for abnormalities.

The volume and the number of samples required for each patient are presented by visit in Appendix 3 – Laboratory Assessments (p 90).

6.3.4. Pharmacokinetic Analyses

PK analyses will be performed in each patient.

The sampling procedure and assay method will be described in the corresponding laboratory manual.

Approximately 2 mL of whole blood will be collected on filter paper by venous puncture for DBS testing at each of the following timepoints:

Ideal timepoint for sampling	Leeway	
D10 3 hours and 7 hours 15 min after last intake of fexinidazole	± 15 min	
D11 24 hours after last intake of fexinidazole	± 1 hour	
D12 48 hours after last intake of fexinidazole	± 1 hour	

- The timing of sample collection was optimised with WinPOPT® software using the parameters of population PK modelling pooled from the DNDiFEX001 and DNDiFEX002 studies. The timepoints for sampling were chosen in order to obtain the best predictions of pre-dose M2 concentrations.
- Lumbar puncture will be performed on D11 24 hours after the last intake of the IP, and the CSF sample will be analysed using dried spot sampling. Dried spot sampling of CSF will be performed on the first 30 patients.

The CSF dried spot samples will be stored under the same conditions (see laboratory manual).

Consequently, only 4 blood samples will be collected: one close to the C_{max} of fexinidazole and M1 and one at the transitional moment between the distribution phase of fexinidazole and M1 and the elimination phase. Both timepoints occur during the "absorption" phase of M2. The other samples will be used to measure the decline in blood fexinidazole, M1 and M2 concentrations.

The pharmacokinetic data collected in children will be incorporated *a priori* in the PK database along with the data in adults, and the consistency between the two populations will be assessed through PK population analysis.

The PK analysis will be performed in the course of the study and the first assessment will be carried out after 6 children weighing between 20 and 35 kg and 6 children weighing less than 35 kg have completed treatment in order to confirm that the target concentrations are reached in the blood and CSF.

CSF sampling will provide data on exposure to fexinidazole in the brain in this population. If the data are consistent with those obtained in adults, i.e. higher than the MIC in CSF, CSF sampling will not be performed in the entire study population. The procedure will no longer be performed after the initial results are available, i.e. after approximately 30 children have been sampled.

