1.9. Pharmacokinetics and Metabolism in Healthy Volunteers

Fexinidazole is well absorbed by the oral route, and rapidly metabolised to the sulfoxide (M1) and sulfone (M2), which account for the largest proportion of drug exposure, regardless of the dose used. Elimination of the second active metabolite is a slow process. C_{max} values for both fexinidazole and M1 are reached in 3 to 6 hours, while M2 levels peak at approximately 24 hours. The mean elimination half-life of fexinidazole and M1 is approximately 10 hours versus approximately 24 hours for M2.

Plasma levels of fexinidazole, M1 and M2 increase in a non-dose-proportional manner with no major changes in their pharmacokinetic profiles.

Urinary excretion of unchanged fexinidazole, M1 and M2 is very low. Fexinidazole, M1 and M2 together account for only 3% of the total dose.

The effects of concomitant intake of food were assessed in two separate studies. In the first study, administration after a standard high-fat meal (FDA recommended) was compared to administration under fasting conditions, and in the second study, two different field meals, i.e. Plumpy'Nut^{®1}, and a traditional meal of rice and beans, were compared to administration under fasting

¹ Peanut-based paste in a plastic wrapper for the treatment of severe acute malnutrition, easily available in the field.

conditions. The observed bioavailability of fexinidazole, M1 and M2 was multiplied by approximately 4-fold with the high-fat meal, and by 2.5- to 3.0-fold with the two field meals (15).

The effect of food on the bioavailability of fexinidazole was taken into account in the design of studies in patients. Indeed, the dosing regimen provides for food intake prior to administration of the IP. This explains why it is particularly important to comply with the instructions on food intake.

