1.11. Choice of Dosing Regimen and Dose

The progression of HAT is identical in adults and children. The choice of the dose in children was therefore based on the results of the analysis of PK/PD data from adults, i.e. healthy volunteers and patients, and on the MIC. The dosing regimen in adults is 10 days of treatment, starting with a loading dose for 4 days followed by a maintenance dose for 6 days. Effective levels of the active drug are rapidly reached using this regimen and are maintained throughout the duration of treatment. Target blood concentrations were reached in adults. Given the PK characteristics of fexinidazole and its metabolites, a similar dosing regimen, i.e. a loading dose for 4 days followed by a maintenance dose for 6 days, can be used in children.

The factors affecting the PK of fexinidazole, such as absorption and maturation of cytochromes and of flavin mono-oxygenase (the main enzyme involved in biotransformation of fexinidazole into its active metabolites), as well as other enzyme systems, are completed before 2 years of age (59). The main metabolic pathways involved in biotransformation of fexinidazole into its metabolites are therefore considered to be the same in adults and in children over 2 years of age. In addition, there is reasonably good proportionality between the dose of fexinidazole administered and the circulating levels of fexinidazole and its metabolites.

The doses of fexinidazole to be administered in children were therefore chosen with the aim of achieving the same levels of systemic exposure, based on the quantity of fexinidazole per unit of body weight. Two points were taken into account:

- Dose administered on Day 1
- Total dose of fexinidazole administered during the entire treatment period.

The main demographic features of the 125 patients (46 women and 79 men) included in the DNDiFEX004 study at the time of the present assessment were taken into account. The age of the patients ranged from 15 to 71 years with a median of 35 years.

Mean body weight was 50.35 kg [34.5-80.0] with a median of 48 kg. It is of note that 15 patients (12 women and 3 men) weighed 40 kg or less with a minimum weight of 34.5 kg.

As mentioned above, the dosing regimen in adults is 1800 mg in a single daily intake for 4 days, followed by 1200 mg in a single daily intake for 6 days, i.e. a total dose of 14,400 mg over 10 days.

Thus:

- mean dose on Day 1 of 35.7 mg/kg [22.5-52.2];

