- mean total dose administered of 28.6 mg/kg/day [18-42].

Overall, male patients are heavier than female patients, and there is therefore a minor difference, i.e. less than 15%, between the mean results in men and in women: 34.8 mg/kg on Day 1 and 27.8 mg/kg/day in men versus 40.4 mg/kg and 32.3 mg/kg/day in women.

In the potential target population of the study, i.e. 29 children diagnosed with HAT during active screening activities carried out to recruit patients to the DNDiFEX004 study, the mean age was 11 years and the mean body weight was 23.4 kg [12-40]. In the NECT-Field study (60), among 65 children between 5 and 11 years of age who were included, mean body weight was 19 kg [9-32] with a median of 18 kg.

If the mean dose on Day 1 is 35.7 mg/kg and the mean total daily dose administered is 28.6 mg/kg, the dose on Day 1 should be $1071 \text{ mg} (30 \times 35.7)$ and the desired total dose administered should be $8580 \text{ mg} (28.6 \times 30 \times 10)$ for a child weighing 30 kg.

Given the usual dosing regimen and the formulations available, i.e. 600-mg tablets, the dosing regimen should be 1200 mg daily for 4 days, followed by 600 mg for 6 days, with a total dose administered of 8400 mg.

Using this dosing regimen, a child weighing 20 kg would receive:

- Dose on Day 1, 60 mg/kg, which is slightly higher than the maximum dose administered on Day 1 in the least heavy adults (52.2 mg/kg);
- Total dose: 42 mg/kg/day, which is exactly the same as the dose administered in the least heavy adults.

In conclusion, in view of the observations above and the fact that the adult the least heavy included in the DNDiFEX004 study weighed 34.5 kg, the dosing regimen is as follows:

- Body weight between [20-35] kg:
 - o 1200 mg from Day 1 to Day 4
 - \circ 600 mg from Day 5 to Day 10
- Body weight \geq 35 kg (same as in adults)
 - o 1800 mg from Day 1 to Day 4
 - 1200 mg from Day 5 to Day 10

Fexinidazole, as 600-mg tablets, will be administered orally, after a meal, i.e. within 30 minutes after the end of the meal.

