4.2. Pre-inclusion / Pre-exclusion Criteria

The pre-inclusion/pre-exclusion criteria can be checked before informed consent is obtained since no study-specific procedures are involved.

Pre-inclusion Criteria

- Between 6 and 15 years of age;
- Body weight at least 20 Kg;
- Male or female;
- Able to ingest at least one complete meal per day (or at least one sachet of Plumpy'Nut[®]);
- Able to swallow the 600-mg tablets of fexinidazole;
- Karnofsky score > 50 (see Appendix 2 Karnofsky Performance Scale; p 89);
- Evidence of trypanosomes in blood and/or lymph and/or CSF;
- Having a permanent address and able to comply with the schedule of follow-up visits.

For the purposes of the study, patients will be stratified based on the following criteria:

Patients with stage-1 HAT

- Trypanosomes in blood and/or lymph
- No evidence of trypanosomes in CSF
- CSF WBC $\leq 5/\mu$ L

Patients with early stage-2 HAT

- Trypanosomes in blood and/or lymph
- No evidence of trypanosomes in CSF
- CSF WBC > $5/\mu$ L and $\leq 20/\mu$ L

Patients with late stage-2 HAT

• Trypanosomes in blood and/or lymph

and

CSF WBC > 20/µL

Or

• Trypanosomes in CSF

The strata will be self-weighted.

Pre-exclusion Criteria

- Body weight strictly less than 20 Kg;
- Severe malnutrition, defined as Body Mass Index < 16. (–2 standard deviation);
- Unable to take medication by the oral route;
- Pregnancy or breast-feeding;
- Clinically significant medical condition (other than HAT) that could, in the opinion of the Investigator, jeopardise the patient's safety or interfere with participation in the study, including, but not limited to significant liver or cardiovascular disease, suspected or proven active infection (including HIV infection), CNS trauma or seizure disorder, coma or consciousness disturbances;
- Severely deteriorated general status, including as a result of cardiovascular shock, respiratory distress or end-stage disease;
- Any condition (excluding HAT-specific symptoms) that affects the patient's ability to communicate with the Investigator as required to complete the study;
- Any contraindication to imidazole drugs, i.e. known hypersensitivity to imidazoles;
- Prior treatment for HAT in the previous 2 years;
- Prior enrolment in the study or prior intake of fexinidazole;
- Foreseeable difficulty complying with follow-up, including family of migrant workers, refugee status, itinerant trader, etc.;
- Active alcohol or drug addiction.

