5.1. Investigational Product

Given the overall dosing regimen and formulation available, i.e. 600-mg tablet, the dosing regimen will be adapted to the child's body weight, as follows:

- Body weight \geq 20 kg and < 35 kg:
 - o 1200 mg from Day 1 to Day 4
 - o 600 mg from Day 5 to Day 10
- Body weight \geq 35 kg (same regimen as for adults)
 - o 1800 mg from Day 1 to Day 4
 - 1200 mg from Day 5 to Day 10

Fexinidazole as 600-mg tablets, will be administered by the oral route, after a meal, i.e. within 30 minutes after starting the meal.

Fexinidazole will be provided by DND*i*, [name].

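### As written, the first PK check and the CSF sampling can be completed with no child in the 35 kg and over dose band, and the meal-timing sentences conflict

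*Protocol*

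**What the plan says.** **Dose bands.** Section 5.1 of the protocol sets two regimens by body weight. From 20 kg to under 35 kg a child takes 1200 mg on Days 1 to 4 and 600 mg on Days 5 to 10. From 35 kg upward the doses are 1800 mg and 1200 mg. The label of this second band reads in part "35 kg (same regimen as for adults".

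**Entry.** Section 4.2 requires "Body weight at least 20 Kg".

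**First PK assessment.** Section 6.3.4 starts it once "6 children weighing between 20 and 35 kg and 6 children weighing less than 35 kg have completed treatment". The stated purpose is "in order to confirm that the target concentrations are reached in the blood and CSF". The same section calls for PK analyses in every patient, from four blood samples, and compares children with adults by population PK. CSF sampling for PK is limited to about the first 30 children. Footnote 2 of Table 3 makes stopping depend on no failure in those 30 and on exposure reaching target.

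**Meal timing.** Section 1.11 places the dose "within 30 minutes after the end of the meal". Section 5.1 places it "within 30 minutes after starting the meal".

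**Proportionality.** Section 1.9 says "Plasma levels of fexinidazole, M1 and M2 increase in a non-dose-proportional manner". Section 1.11 says "there is reasonably good proportionality between the dose of fexinidazole administered and the circulating levels of fexinidazole and its metabolites".

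**The concern.** Two groups of six make sense only if they differ, and here they do not. Taken literally, the trigger counts children from one regimen, and the band on the adult regimen is not named. The check is the protocol's first test of whether children reach the target concentrations, and Section 1.12 already relies on exposure in children being similar to that in adults. Its result also bears on ending CSF sampling, which cannot be made up afterwards for children already treated.

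The meal wording matters because Section 1.9 reports a marked food effect and stresses compliance with the food instructions. Sites that follow different sections would dose at different times relative to the meal, which adds avoidable variation to the exposure data.

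**Working it through.** **1. Weight groups.** Write w for body weight in kg.

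- First group (6.3.4): w between 20 and 35.
- Second group (6.3.4): w < 35. With the entry rule w ≥ 20 (4.2), this becomes 20 ≤ w < 35.
- Lower dose band (5.1): 20 ≤ w < 35.
- Upper dose band (5.1): w ≥ 35.

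Both groups are the lower band. A child of exactly 35 kg could count only if the upper limit of the first group is read as inclusive. Twelve lower-band children meet the trigger.

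**2. CSF.** The first 30 or so children are sampled in order of entry, with no quota by weight. Section 1.11 describes 29 potential target children with a mean of 23.4 kg and a range of 12 to 40 kg. It does not give the share at or above 35 kg, so the number of such children expected among the first 30 cannot be calculated. Nothing in the text requires any.

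**3. Reproducing the plan's per-kg doses (1.11).** With loading dose L and maintenance dose M:

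- Day 1 dose per kg = L / w
- average daily dose per kg = (4L + 6M) / (10w)

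Upper band and adults: 4 × 1800 + 6 × 1200 = 14,400 mg, or 1440 mg/day. Lower band: 4 × 1200 + 6 × 600 = 8400 mg, or 840 mg/day.

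| Weight (kg) | Day 1, mg/kg | Average, mg/kg/day | Stated in 1.11 |
|---|---|---|---|
| 50.35 (adult mean) | 1800/50.35 = 35.75 | 1440/50.35 = 28.6 | 35.7; 28.6 |
| 80 (adult maximum) | 1800/80 = 22.5 | 1440/80 = 18.0 | 22.5; 18 |
| 34.5 (adult minimum) | 1800/34.5 = 52.2 | 1440/34.5 = 41.7 | 52.2; 42 |
| 20 (child) | 1200/20 = 60 | 840/20 = 42 | 60; 42 |

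The plan's figures reproduce within rounding.

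**4. The step at 35 kg.**

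| Weight (kg) | Day 1, mg/kg | Average, mg/kg/day |
|---|---|---|
| 34.9 (lower band) | 1200/34.9 = 34.4 | 840/34.9 = 24.1 |
| 35 (upper band) | 1800/35 = 51.4 | 1440/35 = 41.1 |
| 40 (upper band) | 1800/40 = 45.0 | 1440/40 = 36.0 |

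Ratios at the boundary: 51.4/34.4 = 1.50 and 41.1/24.1 = 1.71. All values in this table lie within the adult ranges of 22.5 to 52.2 mg/kg and 18 to 42 mg/kg/day.

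**5. Can lower-band data stand in for the upper band?** Not directly. Lighter children in the lower band do reach similar doses per kg, but not in the same combination. The average-to-Day-1 ratio is 840/1200 = 0.70 in the lower band and 1440/1800 = 0.80 in the upper. A lower-band child matching the Day 1 dose of a 35 kg child would weigh 1200/51.43 = 23.3 kg and average 840/23.33 = 36.0 mg/kg/day, against 41.1. The absolute doses also differ, by 1800/1200 = 1.5 times in loading and 1200/600 = 2 times in maintenance.

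**6. Meal timing.** Both sections require dosing after food within 30 minutes. One counts from the end of the meal and the other from its start. The fold-changes in Section 1.9 (about 4 with the high-fat meal, 2.5 to 3.0 with field meals) compare fed with fasting intake. They do not measure this difference.

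**7. Proportionality.** Section 1.9 describes healthy volunteers. Section 1.11 offers proportionality as a hedged, additional support for scaling by body weight. Neither gives a dose range or a degree of departure.

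**The case against.** The strongest reply is that this is a slip of the pen. The two dose bands are stated consistently in the Protocol Summary and in Sections 1.11 and 5.1, and two groups of six were plausibly meant to match them. That may be so, but the sentence is the operative rule and the text does not say what was meant.

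A reader might infer that exposure in the upper band goes unconfirmed until the end of the study, or that this check is the only confirmation. The documents do not support either reading. Blood PK is required in every child, is analysed while the study runs and is pooled with adult data; the step in question is only the first assessment. It is also not written as a gate on enrolment or dosing, and the ECG, laboratory and DSMB provisions apply at every weight. No safety harm is shown.

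Two further inferences fail. The 2.5- to 4-fold food effect does not size the meal-timing conflict, for the reason given in the working. The proportionality statements are in tension, but they do not overturn the dose rationale, which also rests on enzyme maturation and shared metabolic pathways.

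On size, the upper band stays within the adult per-kg ranges. The one stated value above the adult Day 1 maximum is 60 mg/kg at 20 kg, in the band that the check does cover. The step at 35 kg comes from the bands and the tablet strength, not from the PK wording. All of this stands.

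Finally, the Protocol Summary reports that the Day 11 lumbar puncture was stopped in October 2014 after approximately 30 patients. New wording cannot recover CSF data. What remains is how the check is described, completed and reported.

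**Conclusion.** The point holds in a limited form. As written, the first PK assessment and the CSF sample can both be complete with no child at or above 35 kg. This rests on the literal text of Section 6.3.4 read with the entry weight. Whether it happened depends on who was enrolled early, which the protocol does not show. The gap is confined to the early check and to CSF exposure.

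The per-kg step of about 50% on Day 1 and 71% on average shows why the bands should be looked at separately. It is not evidence of wrong exposure in either band.

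The meal-timing sentences contradict each other on an instruction the protocol itself stresses; the size of the effect is unknown. The proportionality statements need reconciling, as a lesser matter. Sample size, power and type I error are unaffected.

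**What to change.** - In Section 6.3.4, reconcile the two weight groups with the two dose bands of Section 5.1, so that each band is assessed before the check is called complete.
- Report the early PK results and the available CSF results by dose band, stating how many children at or above 35 kg contributed to each. If none contributed CSF data, say so.
- Reconcile the meal-timing sentences in Sections 1.11 and 5.1.
- Reconcile the proportionality statements in Sections 1.9 and 1.11.

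The sponsor's clinical pharmacology team decides which wording stands in each case; this review does not.

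The cost is wording, and possibly a later first PK assessment if heavier children enter slowly. Because CSF sampling has already stopped, the gain there is limited to assessment and reporting by band.
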